6. INCLUSION AND EXCLUSION CRITERIA*

Child eligibility criteria for enrollment in Asthma Link™ (established clinical program):

- (1) children aged 6-17 years (enrolled in grade 1-12)
- (2) prescribed daily inhaled corticosteroid (ICS) for asthma;
- (3) 1 or more courses of oral steroids in the past 2 years OR 1 or more hospitalizations or ED visits for asthma in the past 2 years OR Asthma Control Test (ACT) score <19 OR 1 or more sick or urgent care visits for asthma (including telehealth) in the last year
- (4) parent/child report of poor ICS adherence on adherence checklist- i.e. child or parent says “Yes” when provider asks if they have difficulty remembering to take their medication or if they regularly take medication holidays or breaks;
- (5) able and willing to assent;
- (6) parental permission
- (7) English or Spanish speaking.

STUDY INCLUSION/EXCLUSION Criteria:

Child Inclusion criteria:

- 1) Meet the eligibility criteria for Asthma Link (as described above) with exception to (7)
- 2) Enrolled in Asthma Link™ (if randomized to the Asthma Link™ Condition)
- 3) Able and willing to provide informed assent
- 4) Must be English or Spanish speaking

Child Exclusion criteria:

- (1) Unable or unwilling to provide informed assent
- (2) Diagnosis of a serious co-morbid illness during the past 5 years
- (3) Developmental delay that would prevent study participation.
- (4) Planning on moving from primary residence or moving outside of the school district in the next 1 year
- (5) A sibling to a child participating in this study

Parent Inclusion criteria are:

- 1) Parent/guardian to patient
- 2) 18 years or older
- 3) Able to understand and communicate in English or Spanish

INVESTIGATOR STUDY PLAN

- 4) Able and willing to provide informed consent.
- 5) May or may not be or become pregnant

Medical Provider Inclusion criteria are:

- 1) Able and willing to provide informed consent

Medical Provider Exclusion criteria are:

- 1) Unable or unwilling to provide informed consent

School Nurse Inclusion criteria are:

- 1) Able and willing to provide informed consent

School Nurse Exclusion criteria are:

- 1) Unable or unwilling to provide informed consent

Asthma Champion Inclusion criteria are:

- 1) Able and willing to provide informed consent

Asthma Champion Exclusion criteria are:

- 1) Unable or unwilling to provide informed consent

Adults lacking capacity and prisoners are also excluded

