11. PROCEDURES INVOLVED*

Randomization. Two groups of two practices (4 practices in total) will be matched based on comparable size and percent of minority patients. Within each pair, practices will be randomly allocated to Asthma Link or the comparison condition, using a computerized function. This will result in two practices randomized to the Asthma Link condition and two practices randomized to the Enhanced Usual Care comparison condition.

Recruitment will be performed from each practice site until the target n=72 parent-child dyads (18 per site) are recruited. (see section 13 on “Sample size calculation”) Recruitment will begin during the 2021-2022 academic school year.

Procedure Steps:

1. Research coordinator (RC) identifies potentially eligible patients (children aged 6-17 years (enrolled in grade 1-12) years and prescribed a daily inhaled corticosteroid per medical record from most recent visit scheduled for a clinic visit) through the practice's office scheduling and medical record system (e.g., Epic). RC will also collect that patient's name, DOB, mailing and email addresses, phone number, insurance type (as a proxy for socioeconomic status), list of

INVESTIGATOR STUDY PLAN

medications, number of emergency room visits, number of hospital admissions and number of oral steroid courses for asthma relief.

2. RC creates a Lilac Form for any potentially eligible patients as described above. (Lilac form is an indicator to the medical provider seeing the patient that this patient is potentially eligible for study.)

3. Asthma Link condition: As part of clinical practice, medical provider will determine if patient is struggling with taking daily asthma medicine. If YES, then will introduce Asthma Link by saying “There is a clinical program that allows for your child to receive their daily asthma medicine at school supervised by the school nurse.” Child can be enrolled in Asthma Link per the usual clinical steps (see Asthma Link steps).

- After they are enrolled in Asthma Link, medical provider will give family one-page description of study (see Flyer) and state “Researchers at UMass are performing a study of children who are participating in Asthma Link, would you be interested in hearing more?”

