3a. Enhanced Usual Care comparison condition: Medical provider will determine if patient is struggling with taking daily asthma medicine, if YES, the provider will give family a one-page description of study (see Flyer) and state “Researchers at UMass are performing a study of children with asthma to learn about how to support them in taking their every day asthma medicine, would you be interested in hearing more?”

- Attached to the “Flyer” will be the Authorization to Contact form. (see Authorization to Contact form)
- If the parent agrees, the Lilac form with the family’s information is faxed to the Research Coordinator. The pediatric office will fax this form with a confidential cover form.
- The fact sheet will be mailed to the parent with a letter saying that the Research Coordinator will call or text them (see Fact Sheet).
- The Research Coordinator will only call the parent five times. The first and third time a message will not be left, but a text message will be sent stating “This is X from Asthma Link, can I call you at TIME?” The second, fourth, and fifth time a message will be left saying “This is X from the University of Massachusetts Medical School. I am calling about the material on Asthma Link I sent you. Please call me back at X.”
- A phone screen will be conducted to ensure study inclusion criteria (see phone script).
- The Research Coordinator will obtain informed consent from eligible participants, including parental permission for their child to participate, child assent to participate, and parental consent to participate. (see sections 30, 31 on Consent)
- After all questions are answered regarding the study by the parent, the Research Coordinator will send the baseline survey via email to the participant to be completed by the parent and child together or will complete the survey over the phone with the child and parent.
- The Research Coordinator will then access the child’s medical record and obtain the discharge summaries, the emergency service records, the office/clinic notes, the problem list, the pulmonary studies, the child’s list of medications, and the child’s height and weight (to help interpret the spirometry data).
- The Research Coordinator will then call the child’s pharmacy to obtain refill history for their daily ICS inhaler.

INVESTIGATOR STUDY PLAN

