SURVEY – MEDICAL PROVIDER – 5 MINUTES _See uploaded medical provider baseline and end-of-intervention surveys. The medical provider survey will include the following constructs: acceptability, cost, and sustainability. All surveys will be completed either on-line using RedCap (please see data management section) or over the phone with the research coordinator. We are using emails and/or phone calls to deliver and collect these surveys.

SURVEY- ASTHMA CHAMPION- 5 MINUTES _See uploaded asthma champion baseline and end-of-intervention surveys. This will include the same constructs of acceptability, cost and sustainability. Surveys will be completed either on-line using RedCap (please see data management section) or over the phone with the research coordinator. We are using emails and/or phone calls to deliver and collect these surveys.

INVESTIGATOR STUDY PLAN

We will be accessing the practice's medical record system (same system as above, e.g., Epic) to obtain documentation of the child's emergency room visits, hospital admissions, and oral steroid courses at the baseline time point (recording the number of events for the 6 months prior), 3 month, 6 month, and 12 month time points (recording the number of each of these events for the 3 or 6 months prior.). This data will also be collected 12 months following the completion of the 12 month survey in order to observe for sustained impact on health outcomes and to see if engagement in Asthma Link continues beyond one year. This data will be directly put into the RedCap database without any downloading of information. (please see data management section)

We will be contacting the child's pharmacy to obtain refill history of their daily ICS medication at baseline (obtaining the number of refills for the prior 6 months), 3, 6, and 12 months, and 12 months following the completion of the 12 month survey to assess for medication adherence. This data will be entered directly into the REDCap database.

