Portable Spirometry: At baseline, 3, 6, and 12 months the child will perform spirometry in the school nurse's office. The Research Coordinator will perform portable spirometry in the school at the time that the student normally reports to the nurse for their daily asthma medication so as not to disrupt the child's school activities. Given that the spirometry test takes less than 3 minutes to complete for each child, we are confident that it will not pose a disruption to the child's school activities. The Research Coordinator will enter the spirometry data into RedCap for each participant without downloading any data.

School absence data will be collected through school nurse report and will be recorded from the school nurse on the School Nurse checklist and faxed to the Research Coordinator.

Asthma Link Condition: Those practices that are randomized to the Asthma Link group will receive pediatric pulmonologist delivered trainings for pediatric practices on behavioral strategies to help promote asthma medication adherence and a 1 hour training on the Asthma Link clinical program and how to enroll children in Asthma Link (reviewing the steps of this clinical program- see "Asthma Link Clinical Program Steps") and carry out this evidenced-based program in the context of their clinical practice (reviewing the steps to Asthma Link and answering any questions they may have).

Comparison Condition: Those practices that are randomized to the Enhanced Usual Care Comparison Group will receive pediatric pulmonologist delivered trainings for pediatric practices on behavioral strategies to help promote asthma medication adherence. These include training to counsel patients on the strategies such as the placement of cell phone alarms to remember to take their daily medicine and placement of an elastic band around the inhaler and the toothbrush so that a child always remembers to take their daily inhaler before brushing their teeth. We thought it ethically important to provide more than just usual care to the 2 pediatric practices assigned to the comparison condition.

Families who agree to participate in the study from either the Asthma Link or Enhanced Usual Care practices will receive a mailed "Asthma Workbook" to aid in their understanding of asthma, support their asthma care and help with daily medicine adherence (See Asthma Workbook)

INVESTIGATOR STUDY PLAN

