- Risk of Spirometry: Spirometry is a routine, non-invasive clinical test that is commonly performed in children with asthma. This test has been used both clinically and in research without any adverse events.^{23,24} There are no risks associated with spirometry except for the potential for a slight dizzy feeling and/or temporary cough. These symptoms are not always present and are temporary. In order to minimize risks, the participant will be in a seated position with adult supervision and a trained technician will perform spirometry, with physician available by phone for concerns or questions. We will follow institutional policies for prevention of Covid transmission, which includes the technician wearing a surgical mask with eye protection and using a new disposable mouthpiece for each participant. For this study the test is performed without the intent of yielding direct health benefit.
- Risk of discomfort while answering questions: Some subjects may feel uncomfortable answering certain survey questions (e.g., questions about family income) however subjects will be notified that they are welcome to skip questions or withdraw from the study at any time without penalty.

Given that this is a minimal risk study, the only foreseeable risks to the subjects include the possible loss of confidentiality. To address this, all participants will be given information on ways to contact [name] and the University of Massachusetts Medical School IRB

Data and Safety Monitoring Board (DSMB)

Given that this is a minimal risk study (wherein participants agree to enroll in the study after they become part of the Asthma Link program if they are in the Asthma Link practices or after they fit study inclusion criteria if in the Enhanced Usual Care practices), participants will primarily be evaluated through surveys, interviews, and spirometry, and therefore a data monitoring committee and/or a data safety monitoring board is not appropriate for this study. Alternatively, the PI will periodically examine the data and should any research-related unexpected events arise, the PI will evaluate the event per the procedure listed above and will adhere to the institution's prompt reporting requirements. We do not anticipate any adverse events from this study as the primary procedures involve minimal risk surveys, checklists and routine clinical spirometry.

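### Programme enrolment comes before consent and baseline in the Asthma Link arm only, so that arm's baseline can include supervised treatment and its follow-up clock can start late

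*Combined protocol and SAP*

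**What the plan says.** **Order in the Asthma Link arm.** Section 11, step 3, has the provider enrol the child in the programme at the visit and then introduce the study: "After they are enrolled in Asthma Link, medical provider will give family one-page description of study". Section 6 makes programme membership a study inclusion criterion for this arm: "Enrolled in Asthma Link™ (if randomized to the Asthma Link™ Condition". The DSMB paragraph of Section 14 repeats the order: "participants agree to enroll in the study after they become part of the Asthma Link program if they are in the Asthma Link practices".

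**Order in the comparison arm.** In step 3a the flyer follows directly from the adherence question: "if YES, the provider will give family a one-page description of study (see Flyer". No supervised dosing comes before it.

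**From flyer to baseline.** Section 11 then lists the faxed form, the mailed fact sheet, the calls ("The Research Coordinator will only call the parent five times"), the phone screen and consent. Only after these is it said that "the Research Coordinator will send the baseline survey via email to the participant", followed by the record review and the pharmacy call. Section 24 adds an electronic HIPAA signature before the survey. No maximum number of days is given.

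**Anchor.** Section 13 defines baseline as study entry. Section 11 takes the record-based counts "at the baseline time point (recording the number of events for the 6 months prior" to that point, and pharmacy refills likewise. Spirometry, at baseline and at each follow-up, is done in the nurse's office "at the time that the student normally reports to the nurse for their daily asthma medication".

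**Analysis.** Section 13 compares arms by t-test or Poisson regression. It does not say whether baseline will be used for change scores or adjustment. It calls the health outcomes exploratory, and lists effect size, SD and ICC among the quantities the pilot is to supply.

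**The concern.** A baseline should describe the child before the intervention. Here its date is set by how long recruitment paperwork takes, while the programme can already be running. This can happen in one arm only, because the comparison arm has no supervised dosing to start early. (The adherence training goes to practices in both arms, so counselling before baseline is not one-sided by design.)

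Three things follow for a child whose first supervised dose precedes baseline:

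- ACT, symptom days and FEV1 at baseline already contain part of any benefit.
- Events and refills between programme start and study entry are counted as pre-programme and are lost from follow-up.
- The 3-, 6- and 12-month points fall later in programme time than their labels say.

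At stake are the baseline comparison between arms, any change-score or adjusted contrast, and the effect-size and SD inputs to the larger trial.

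**Working it through.** The plan states no interval from programme start to baseline, so there is no figure to reproduce. The check has two parts: the order of steps, and what a given lag would do.

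**1. Order of steps**

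| Step | Asthma Link | Enhanced Usual Care |
|---|---|---|
| Adherence question at visit | yes | yes |
| Enrolment in supervised programme | at the visit | none |
| Study flyer | after enrolment | after the question |
| Fax, mailing, up to 5 calls, screen, consent | next | next |
| Baseline survey, records, refills | next | next |

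The first supervised dose has no fixed place in this sequence. Section 5 says families bring the inhaler to school. Dosing can therefore begin before or after baseline, and nothing in the plan orders the two.

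**2. Event look-back (hypothetical lag)**

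Let L be the weeks from first supervised dose to baseline. The look-back is 6 months, or 26 weeks. The illustrative effect is the 54% fall in ED visits from the pre/post study in Section 5, taken as immediate.

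- Share of look-back under the programme = L/26
- Understatement of baseline count = 0.54 × L/26
- Apparent decline = 1 − 0.46/(1 − 0.54 × L/26)

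| L (weeks) | Share exposed | Understatement | Apparent decline (true 54%) |
|---|---|---|---|
| 0 | 0% | 0% | 54.0% |
| 2 | 7.7% | 4.2% | 52.0% |
| 4 | 15.4% | 8.3% | 49.8% |
| 8 | 30.8% | 16.6% | 44.8% |
| 12 | 46.2% | 24.9% | 38.7% |

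**3. ACT, symptom days and FEV1 (hypothetical)**

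Let f be the fraction of the follow-up effect already present at baseline in the Asthma Link arm, and ρ the within-arm slope of follow-up on baseline with equal variances. The share of the true effect kept is 1 for a follow-up-only comparison, 1 − f for change from baseline, and 1 − ρf for baseline adjustment.

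| f | Follow-up only | Change score | Adjusted, ρ = 0.5 |
|---|---|---|---|
| 0 | 100% | 100% | 100% |
| 0.10 | 100% | 90% | 95% |
| 0.25 | 100% | 75% | 87.5% |
| 0.50 | 100% | 50% | 75% |

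To link f to a lag, assume benefit accrues as e(t) = 1 − 0.5^(t/h), with half-time h of 4 or 8 weeks. A change score taken 13 weeks after baseline then recovers [e(13+L) − e(L)]/e(13+L):

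- L = 0: 100%.
- L = 2: h = 4 gives (0.926 − 0.293)/0.926 = 68%; h = 8 gives (0.727 − 0.159)/0.727 = 78%.
- L = 4: h = 4 gives (0.947 − 0.500)/0.947 = 47%; h = 8 gives (0.771 − 0.293)/0.771 = 62%.

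Neither L nor h is in the documents. If the programme helps, every distortion in parts 2 and 3 is toward no difference.

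A follow-up-only comparison escapes the subtraction, but it measures the Asthma Link child at 3 months plus L on the programme.

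**The case against.** The strongest reply is that enrolment is not exposure. The plan itself treats delivery of the inhaler as uncertain: Section 10 surveys families on obtaining two inhalers and getting one to school. Some, perhaps many, baselines will be clean. This stands, and the point is worded accordingly.

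A reader might infer from the spirometry sentence that baseline FEV1 is always taken after dosing has begun. The documents do not support that. The sentence covers all four time points and sets a time of day chosen to avoid disrupting school. It is also not limited to Asthma Link children, although comparison children have no programme dose to report for.

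A reader might also infer that the plan captures nothing about when dosing starts. It does capture something: Section 10 lists nurse records of daily attendance and of medicine brought in. What is missing is a named first-dose date tied to baseline. The forms themselves are uploads not available for this review.

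Events are more recoverable than symptom scores or FEV1. Step 1 of Section 11 collects ED visits, admissions and steroid courses before the visit in both arms, though with no stated window and not as the baseline. Discharge and emergency records are obtained later, so events could probably be re-anchored. This limits the harm for counts but not for ACT, symptom days or FEV1.

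Finally, the health outcomes are exploratory, no change-score analysis is promised, and Section 13 says pilot effect sizes are imprecise and will be combined with outside results. All of this stands. It lowers the stakes without removing the asymmetry.

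**Conclusion.** The point holds as a should-fix. The order of steps is stated in Sections 6, 11 and 14, and baseline is set at study entry without a cap on the interval, so one arm's baseline can include supervised treatment and its clock can start late.

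The size is unknown and may be zero. The percentages above depend on an assumed lag, an assumed speed of response, and an analysis that uses baseline; the last is an option the plan leaves open, not one it commits to. Counts are modestly exposed at short lags. ACT, symptom days and FEV1 could be more so, and cannot be recovered once dosing has started.

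It would go too far to say that the trial's main conclusions are biased. Recruitment, retention and fidelity, the primary outcomes, are not affected.

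**What to change.** 1. In both arms, define time zero as the index clinic visit at which the study flyer is given. End the six-month event and refill look-back at that date, and count follow-up event and refill windows from it.
2. Take the date of the first school-supervised dose from the school nurse log. Report the interval from it to the baseline survey and to baseline spirometry.
3. For ACT, symptom days and FEV1, make the unadjusted follow-up comparison the main exploratory contrast. Give baseline-adjusted or change-score results as a sensitivity analysis that flags children whose baseline came after the first supervised dose, without excluding them. Excluding them would remove children from one arm only, according to how quickly they started.

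This resets the clock for event and refill windows. For the survey and spirometry measures it makes the delay visible but does not remove it.

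The costs are slightly more data entry, some lost precision, and some children shown to have no clean symptom or FEV1 baseline. On precision: at the illustrative ρ = 0.5, and ignoring clustering, adjustment would leave 1 − 0.25 = 0.75 of the variance, so the unadjusted standard error is about 1/√0.75 = 1.15 times as large. The clinical start of the programme is unchanged, and so is the sample size.

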24. LOCAL RECRUITMENT METHODS

Justify the feasibility of recruiting the required number of suitable subjects within the given recruitment period. For example, how many potential subjects do you have access to? What percentage of them do you need to recruit?

Feasibility of Recruitment: Rates of asthma approximately range from 15%-25% among the practices' patients, with a mean of 18.5%. Given this rate and number of patients, we are very confident that we will be able to recruit 13 families per practice over the course of the one and a half-year recruitment period.

Describe when, where, and how potential subjects will be identified and recruited. If recruiting in a clinical setting, will clinical staff ask potential subjects if it's ok for study staff to approach? If recruiting by mail, will letters come from the subject's clinician or clinic head?

For the sites that are randomized into the intervention arm of the study, a one page flyer for the clinical Asthma Link™ program will be placed in each of the exam rooms in the clinics and will encourage families to ask their providers about Asthma Link™ if they have a child who has asthma. The flyer will only advertise the clinical Asthma Link™ program. Additionally, triage nurses at these sites may remind providers to screen potentially eligible patients for the clinical Asthma Link™ program when scheduling sick visits related to Asthma or breathing

INVESTIGATOR STUDY PLAN

problems. During the clinic visit, the pediatric provider will give the family a one-page description of the study and, if interested, will send a referral to the study. Research staff will mail the family the fact sheet and HIPAA authorization, contact them by phone to explain the study, and obtain verbal consent for those interested. Research staff will send an email link to access the survey to families who provide verbal consent. The 4 pediatric practices participating in the trial estimate 7,462 children total in their practices between children in grades 1-6; with a conservative estimate of 15% with asthma symptoms, this provides approximately 1,119 children from which to recruit 40 children into the trial, making recruitment highly feasible.

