Describe how individuals will be screened for eligibility. Will any identifiers be recorded? If so, when will identifiers be de-linked from the data and when will identifiers be completely destroyed? Be sure to address individuals who enroll and individuals who turn out to be ineligible or who decline to participate.

The fact sheets and the HIPAA authorization form will be mailed to the potential participants with a letter saying that the Research Coordinator will call them. The Research Coordinator will contact the parent by phone to explain the study and describe the parent/legal guardian and child's potential role using a standardized information sheet. The Research Coordinator will answer any questions about the study and **obtain** verbal consent. Once the parent provides consent, the Research Coordinator will obtain verbal assent from the child. The Research Coordinator will then email the link to sign the HIPAA authorization. Once the HIPAA authorization is signed, the Research Coordinator will then email the link to complete the survey via REDCap. The Research Coordinator will only call the family five times. The first time a message will not be left. The second, fourth and fifth time a message will be left saying "This is X from the University of Massachusetts Medical School. I am calling about the material I sent you. Please call me back at X. (please see uploaded flyer and phone script). Enrollment will not begin until IRB has approved these materials. Individuals who decline to be contacted or who decline to participate in the study will not be contacted.

Describe the amount, method, and timing of any payments to subjects.

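### The contact script in Section 11 names Asthma Link to comparison families before consent, while Section 24 gives the same voicemail without the name

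*Combined protocol and SAP*

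**What the plan says.** Section 11 allocates by practice: "Within each pair, practices will be randomly allocated to Asthma Link or the comparison condition". Families are approached after that, and the provider's words differ by arm. In Asthma Link practices, once the child is in the programme, the provider says "Researchers at UMass are performing a study of children who are participating in Asthma Link". In Enhanced Usual Care practices (step 3a) the provider says "Researchers at UMass are performing a study of children with asthma to learn about how to support them" with daily medicine, and the programme is not mentioned.

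The contact steps follow as bullets under step 3a. The coordinator may call up to five times. Calls one and three leave no voicemail but are accompanied by a text: "This is X from Asthma Link, can I call you at TIME". Calls two, four and five leave a voicemail in which the coordinator gives the university's name and adds "I am calling about the material on Asthma Link I sent you". No separate version is given for either arm.

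Section 24 describes the same sequence of calls. Its voicemail also opens with the university's name but continues "I am calling about the material I sent you". It mentions no text message. The same section describes programme advertising for intervention practices only: "For the sites that are randomized into the intervention arm of the study, a one page flyer for the clinical Asthma Link™ program" is to go in exam rooms there.

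Section 4 lists recruitment and retention among the primary trial outcomes, and the Section 10 table counts refusals and their reasons. Section 30 says the study is explained fully during the consent call.

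**The concern.** Two current sections give the coordinator different words for the same voicemail, and the version in Section 11 carries the name of the intervention to families whose practice does not offer it. An Asthma Link family already knows that name from its provider. A comparison family has been told only of university researchers studying adherence support, and may then receive a text from a sender it does not recognise.

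The messages arrive before consent, when families decide whether to answer, call back or decline. Recruitment and reasons for refusal are among the things this pilot exists to measure, so an avoidable difference in how the approach is understood in the two arms is unwelcome. Some comparison families might also ask about a programme they had not otherwise been told of.

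**Working it through.** No arithmetic applies, because the plan gives no figure on this point. The check is a comparison of the wording at each step.

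| Step | Asthma Link arm | Enhanced Usual Care arm |
|---|---|---|
| Exam-room flyer (Section 24) | Programme flyer | None described |
| Provider introduction (Section 11, steps 3 and 3a) | Programme named | Programme not named |
| Text with calls 1 and 3 (Section 11) | No separate version | Programme named as the sender |
| Voicemail at calls 2, 4 and 5 (Section 11) | No separate version | Programme named as the subject of the mailing |
| Voicemail (Section 24) | Not named | Not named |
| Consent call (Section 30) | Full description, no limit by arm | Full description, no limit by arm |

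1. *Do comparison families receive the Section 11 messages?* Yes. The bullets sit under step 3a. If they apply to that step alone, they are addressed to comparison families. If they apply to both arms, comparison families are included.

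2. *Do the sections conflict?* Yes. The voicemails differ in whether they name Asthma Link, and the text message appears in Section 11 only. This needs no inference about intent.

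3. *What is disclosed?* The programme's name. Neither message mentions school, a nurse or supervised dosing.

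4. *When?* After the family has agreed to be contacted and before the consent conversation. Response and refusal are the outcomes most directly open to influence.

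5. *How many families?* This cannot be derived. Five is a limit on call attempts. The scripts are most naturally read as following unanswered calls, so a family that picks up the first call may receive neither message, while a family that never enrols may receive several.

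**The case against.** The strongest reply is that the name adds little. It is in the study title, so the coordinator may simply be identifying the study. The plan claims no blinding of families. The consent call covers the whole study, so comparison families may learn of the programme minutes later. Recruitment already differs openly by arm: intervention families are approached after joining the programme, and flyers and triage reminders are described for those practices only. Much of this stands, and it is why the point is minor. It does not remove the conflict between Sections 11 and 24, and it does not cover the period before consent.

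Three stronger readings are tempting, and the documents support none of them.

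- *That the comparison wording was written to conceal the programme, and the script defeats that.* No reason for the omission is stated. The Asthma Link introduction speaks of children already taking part, which would be untrue in a comparison practice, so different wording was needed in any case.
- *That every comparison family hears the name at all five contacts.* This would mean 36 families (Section 13), or 2 practices × 25 dyads = 50 at full enrolment (Section 25). It treats a limit on call attempts as exposure, and counts enrolled families when the messages go to everyone who agreed to contact.
- *That the arm difference is diluted, or that retention and parent-reported outcomes are biased.* Under Section 5, entry to the programme runs through a pediatrician's order to the school nurse, and no route without that order is described. Retention and parent reports come after the consent explanation, and nothing shows that an earlier mention of the name changes them.

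**Conclusion.** The point holds as a minor one. Section 11, as written, sends the programme's name to comparison families before consent, and Section 24 contradicts it. A differential effect on response and refusal is plausible, as are some enquiries about the programme, but the documents allow neither to be sized.

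This rests on two assumptions: that coordinators would follow Section 11 literally, and that the mailed letter and fact sheet do not already name Asthma Link to comparison families. Those materials and the phone script are not in the documents. If they do name it, changing the messages alone would remove little of the exposure, and the mailing is the place to look. If they do not, the Section 11 voicemail misdescribes what was sent.

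**What to change.** Reconcile Sections 11 and 24 with one text and one voicemail used in both arms. Identify the caller by the university's name in each, and take the voicemail wording from Section 24. State in both sections whether a text is sent and after which calls. Then check that the letter and fact sheet for comparison families are consistent with that wording.

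The cost is a script edit with IRB notification. The design, sample size and analysis are unaffected.
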